Subjects who are deemed eligible, but are unable to commit to 3 - 4 weeks of inpatient treatment will be seen 2 times per week in outpatient treatment at the Yale Stress Center at [name]. Outpatient appointments will include motivational enhancement, urine drug screens, breathalyzers, blood pressure monitoring, and counseling. Daily interactive voice response (IVR) telephone monitoring, or the smartphone app MetricWire, will prompt subjects to take study medication, and assess their alcohol use, craving, craving resistance and mood states. Blood draws will be done at weeks 4-5 to measure Prazosin levels. These levels will allow staff to ensure subjects are taking medication as prescribed. Medication compliance will also be monitored through the use of riboflavin as a marker. Riboflavin produces a bright yellow discoloration of the urine when the medication is taken 2 to 8 hours prior. After the first week all subjects will be taking morning and bedtimes doses of the medication. After this time, staff will easily be able to visually inspect the subject's urine to determine whether the morning dose has been taken. 25mg of riboflavin will be added to all doses of Prazosin and placebo by the pharmacist when capsules are made. Thirty-two cc's of whole blood will be also collected from patients at intake for the purposes of understanding genetic factors that may affect craving.

In the event that someone is unable to achieve any period of abstinence within a 4-week period, they will be offered inpatient treatment or referred to a higher level of care at another facility. In the event that someone achieves abstinence but has occasional relapses, outpatient treatment will continue until they either sustain abstinence or a higher level of care is clinically indicated. These clinical judgments will be made by the principle investigator. Subjects will be provided with dollar amounts for kept appointments. Rewarding subjects for kept appointments, regardless of whether their urine is clean or not, will enable us to maintain treatment compliance while allowing for test of efficacy of medication in this trial.

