For both HPA and catecholamine assays, data will be analyzed for the time-points outlined in Table 3. In addition, as each measure may show different response profiles over time, we will also assess maximal or peak response and area under the curve (AUC) for each measure. Peak and AUC assessments of these measures are commonly used methods to reduce variability in responses and have been used in several studies (Kirschbaum, Wust, Faig, & Hellhammer, 1992; O'Malley, Krishnan-Sarin et al. 2002).

Standard Individual Drug Counseling: All subjects will participate in weekly standard individual drug counseling as outlined in the Individual Drug Counseling Manual (IDC, Mercer & Woody, 1994) during the outpatient trial. Each subject will be assigned a counselor with expertise in IDC who will see the patient for the 9 or 12 week outpatient trial. The general purpose of the counseling sessions as described in the manual are to: (1) acquire information about important concepts and aspects of recovery from alcohol addiction; (2) increase self-awareness of specific problems and issues in relation to addiction and recovery, and (3) learn new coping skills to deal with problems contributing to or resulting from the addiction and to improve functioning. The focus of this psycho-educational approach is on providing patients with frequent supportive contact, introduce them to key concepts about the recovery approach, and develop a sense of personal responsibility for recovery.

Assessments: A trained research assistant will meet with the client at various time-points to assess the client on selected substance use and psychological functioning measures using structured interviews, self-report assessments and to obtain urine samples for toxicology screens. A description of the assessment battery follows, and Table 1 lists the schedule of administration of assessments.

Screening Assessments:

Sociodemographic/general patient information. Demographic data, medical history, and family psychiatric history will be assessed with interviews and self-report forms that provide data on age, race, socioeconomic status, marital status, psychiatric family history, educational and occupational levels, and significant medical history.

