Prazosin (marketed by Pfizer) is an alpha-1-adrenergic agonist, that is known to preferentially bind to post-synaptic alpha1-adrenergic receptors that are highly concentrated in the prefrontal cortical regions (Taylor & Raskind, 2002). It has been shown to have beneficial effects on PTSD symptoms (Taylor et al., 2006; Taylor & Raskind, 2000) and recent data has supported it's use in alcohol/cocaine dependence (Simpson et al., in press; Zhang & Kosten, 2005). The major advantage that Prazosin has over clonidine is that it is less sedating and with less hypotensive effects than clonidine. More specifically, Clonidine is a non-selective agonist of alpha 2a, 2 b and 2c receptors, which accounts for its sedative and hypotensive effects. Conversely, Prazosin and guanfacine are preferential for the alpha-1 and alpha-2a receptors respectively; thus, limiting sedative and hypotensive effects (Arnsten et al., 1988). Additionally, the plasma half life of Prazosin is 2-3 hours, compared to 4-10 hours for clonidine (Physician Desk Reference, 2007), allowing rapid titration and limiting accumulation of the drug.

Studies using Prazosin in patients with PTSD and alcohol dependence have used doses ranging from 2 to 16 mg/day. Commonly reported side effects with Prazosin have been fatigue, sedation and light-headedness, which are generally rated as mild in intensity. Possible side effects commonly associated with Prazosin include: low blood pressure, some drowsiness, dryness of mouth and/or throat and dizziness. No serious side effects have been noted in adult populations. There is no evidence that Prazosin will pose a greater risk to the pilot study population. Subjects will not be started on the study medication until no alcohol is present in their system. Throughout the study, subjects will be monitored for alcohol consumption. If a subject were to resume using alcohol, study medication will be discontinued.

iii) Laboratory Sessions:

(a) Intravenous (IV) Catheter: When an IV is started, there is some risk that subjects may develop a bruise or bleeding where the vein is punctured. If this occurs, appropriate treatment will be instituted immediately. On extremely rare occasions, fainting, blood clot or infection may occur.

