The principal investigator will be responsible for monitoring the data, assuring protocol compliance, and conducting the safety reviews at the specified frequency, which must be conducted at a minimum of every 6 months (including when reapproval of the protocol is sought). During the review process, the principal investigator (monitor) will evaluate whether the study should continue unchanged, require modification/amendment, or close to enrollment. Either the principal investigator, the IRB or DSM, have the authority to stop or suspend the study or require modifications.

2. The risks associated with the current study are deemed greater than minimal for the following reasons:

We do not view the risks associated with the withdrawal of alcohol as minimal risks. Although we have assessed the proposed study as one of greater than minimal risk, the potential exists for anticipated and/or unanticipated adverse events, serious or otherwise, to occur since it is not possible to predict with certainty the absolute risk in any given individual or in advance of first-hand experience with the proposed study methods. Therefore, we provide a plan for monitoring the data and safety of the proposed study as follows:

3. Attribution of Adverse Events:

Adverse events will be monitored for each subject participating in the study and attributed to the study procedures / design by the principal investigator, [name] according to the following categories:

- a.) Definite: Adverse event is clearly related to investigational procedures(s)/agent(s).
- b.) Probable: Adverse event is likely related to investigational procedures(s)/agent(s).
- c.) Possible: Adverse event may be related to investigational procedures(s)/agent(s).
- d.) Unlikely: Adverse event is likely not to be related to the investigational procedures(s)/agent(s).
- e.) Unrelated: Adverse event is clearly not related to investigational procedures(s)/agent(s).

4. Plan for Grading Adverse Events:

The following scale will be used in grading the severity of adverse events noted during the study:

1. Mild adverse event
2. Moderate adverse event
3. Severe

5. Plan for Determining Seriousness of Adverse Events:

Serious Adverse Events:

In addition to grading the adverse event, the PI will determine whether the adverse event meets the criteria for a Serious Adverse Event (SAE). An adverse event is considered serious if it results in any of the following outcomes:

1. Death;

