3). [name] is an Associate Professor at the Department of Psychiatry at Yale University. She is PI and Co-PI on several NIH funded studies examining at risk adolescents, addiction treatment and the neuroscience of addiction.

The DSMB members will evaluate all Adverse and Serious Adverse Events, and will assist the PI in preparing and sending the pertinent expedited reports to the appropriate persons as outlined below. They will monitor the study quarterly and review all adverse event sheets completed during that period. They will assist the PI in making critical decisions regarding a particular subject continuing in a study for safety reasons. They will review the summary of all Adverse Events for this study, which will be reported annually to the Yale Human Investigation Committee (HIC) and study sponsors.

12. Statistical Considerations: Describe the statistical analyses that support the study design.

Power Analysis: Sample size estimates for the laboratory study is based on our preliminary study of Prazosin (Fox et al., 2011) and previous pilot trials of Prazosin (Simpson et al., 2009). Moderate to large effect sizes were obtained for significant interaction effects in alcohol craving (2-way: $f = .44$; 3-way: $.81$), anxiety (2-way: $f = 1.16$; 3-way: $.87$) and Cortisol/ACTH ratio (2-way: $f = .83$ and $f = .71$; 3-way: $f = .65$). A conservative effect size of $f = .44$ for detection of significant interactions, and with power = .80, with $p < .05$, sample size estimates (Cohen, 1988, p.384) indicated that we would require 18 subjects per cell to detect the specified interaction hypotheses of the laboratory study. Including a 5-10% attrition rate, we estimated that 20 subjects per cell would provide adequate power to test the laboratory aims.

Sample size estimates for the clinical trial outcomes were determined from effect sizes derived from Simpson et al (2009). In this study, 6/7 PZ subjects remained abstinent and drank an average of 3.2 drinking days/wk after achieving full dose compared to the PL group where 4/10 were abstinent and drank on 5.5 drinking days/wk. These data yielded large effect sizes ($d = 1.26$ for mean drinking days; and $w = 1.23$ for proportion abstinent). As we proposed a 2X 2 design

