Outpatient subjects will come in for 2x weekly appointments and complete motivational enhancement, urine drug screens, breathalyzers, blood pressure monitoring, and counseling. Medication compliance will be monitored by blood draws done at week 4-5, to measure Prazosin levels, and through the monitoring of riboflavin as a urine marker. Riboflavin produces a bright yellow discoloration of the urine when the medication is taken 2 to 8 hours prior. After the first week all subjects will be taking morning and bedtimes doses of the medication. After this time, staff will easily be able to visually inspect the subject's urine to determine whether the morning

dose has been taken. 25mg of riboflavin will be added to all doses of Prazosin and placebo by the pharmacist when capsules are made.

Outpatient subjects will self-administer study medication, and will be reminded via daily interactive voice response (IVR) telephone monitoring or through the smartphone app MetricWire. Daily IVR telephone monitoring or MetricWire will be used to prompt patients to take study medication, and also to assess alcohol use, craving, craving resistance and mood states. Concordance between daily IVR or MetricWire reports and alcohol positive urines will be evaluated for daily versus retrospective reporting.

The MetricWire app (developed and owned by MetricWire Inc), has previously been utilized in clinical and academic research, and is HIPPA compliant. Subjects will complete a training session where we will assist them in installing the app on their smartphone device. At the end of the study, we will assist subjects in removing the app from their smartphone. If a subject does not own a smartphone, one will be supplied for their use, for the duration of the study, once a separate smartphone agreement is understood and signed.

We expect most subjects will tolerate a dose of 16mg. However, subjects who cannot tolerate a dosing schedule of 16mg will meet with the study psychiatrist to discuss a lower dose. Subjects who cannot tolerate a minimum dose of 16mg will be maintained on maximum tolerated dose of Prazosin (up to 16.0 mg/day) and during week 12 the medication will be tapered down to 0 over the course of seven days. Some patients may be tapered prior to week 12.

All study staff will remain blind to medication condition. Randomization will be conducted by the CMHC Pharmacy / YNHHS IDS, which have extensive experience in random assignment of patients in medication trials.

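### Staff are told to check outpatient compliance with week 4-5 prazosin levels and also to stay blind; the plan does not say who receives the levels or when

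*Combined protocol and SAP*

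**What the plan says.** The Outpatient Plan (Section V, item 3) schedules a blood draw at weeks 4-5 for prazosin levels and gives its purpose: "These levels will allow staff to ensure subjects are taking medication as prescribed". Section VI, A.3 (Source) says the same for outpatients: "Medication compliance will be monitored by blood draws done at week 4-5, to measure Prazosin levels". The same item later sets the blinding rule, with no exception: "All study staff will remain blind to medication condition". It gives randomization to the pharmacy / investigational drug service, but does not name that service as recipient of the levels.

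Both sections also describe a second compliance check. Riboflavin, 25 mg, goes into every active and placebo capsule, and staff look for discoloured urine.

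Section VIII lists prazosin levels among the research data (item a). Its statement on who may access de-identified data (item f) makes no exception for them.

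**The concern.** A drug level carries information on allocation in a way that riboflavin does not. Staff who use the level during treatment to check compliance learn the arm of every subject with a detectable result. Staff who stay blind cannot use the level for the purpose the plan gives it.

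Three roles that depend on blinding continue after weeks 4-5:

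- **Adverse events.** Section V, item 11 has events "attributed to the study procedures / design by the principal investigator".
- **Level of care.** For outpatients who reach abstinence but relapse occasionally, the Outpatient Plan says "outpatient treatment will continue until they either sustain abstinence or a higher level of care is clinically indicated", and leaves the judgment to the principal investigator.
- **Drinking data.** The Assessments text says: "A trained research assistant will meet with the client at various time-points to assess the client on selected substance use" and other measures. The assessment schedule (Table 1) names the research assistant as rater for the Substance Use Calendar. Section V, item 12 makes that calendar one source for both primary outcomes, heavy drinking days and any drinking days.

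**Working it through.** The plan gives no figure to reproduce here, so the check is mainly a comparison of passages.

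**1. What a level reveals.** The dosing table in Section V, item 3 plans 75 subjects on prazosin and 75 on placebo. Placebo subjects receive no prazosin, so P(prazosin | detectable level) = 1. A fully adherent placebo subject has no level, so the assay can never confirm adherence in that arm.

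**2. How much of the blind a reader of the levels would lose (illustration).** Let *a* be the share of assayed prazosin subjects with a detectable level. The documents do not give it, so it is assumed here, as is 1:1 allocation among outpatients.

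- P(placebo | undetectable) = 0.5 / (0.5 + 0.5(1 − *a*)) = 1/(2 − *a*)
- Share of arms guessed correctly = 0.5 + 0.5*a*

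| *a* (assumed) | P(placebo given undetectable) | Arms guessed correctly |
|---|---|---|
| 0.5 | 1/1.5 = 0.67 | 75% |
| 0.7 | 1/1.3 = 0.77 | 85% |
| 0.9 | 1/1.1 = 0.91 | 95% |

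An intact blind gives 50%. The table describes someone who sees the levels; it does not say that anyone does.

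**3. Who receives the levels.** Section V, item 3 says staff, without a role. Section VI, A.3 says compliance is monitored and names no reader. The laboratory text in Section V names laboratories for the hormone, saliva and catecholamine samples only. No section available for this review names an unblinded recipient, masks the result or delays it. Some pages, including those after the research team heading in Section III, were not available, so a role listed there could not be checked.

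**4. Longest possible exposure.** The earliest draw is at the start of week 4, after 3 completed weeks. With results on the same day, 12 − 3 = 9 weeks remain, and 9/12 = 75%. The last of these is the taper week. A later draw or any assay turnaround shortens the period; the plan states no turnaround.

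**5. What cannot be computed.** The split of the 150 subjects between inpatient-outpatient and outpatient plans is not given. Nothing in the documents allows the bias in either primary outcome to be estimated.

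**The case against.** The best defence is that this is an unstated routing step. The pharmacy prepares the capsules and conducts randomization, so someone already holds the allocation and could read the levels. The explicit blinding rule would then govern the looser word for staff in the Outpatient Plan. Neither section says that results return to the clinic during treatment.

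Part of this stands. An unblinded reader, or release after database lock, would remove the conflict. But the plan provides for neither, the blinding rule covers all study staff, and making sure that subjects are taking their medication describes use during treatment.

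The consequences are also limited. On adverse events, "The DSMB members will evaluate all Adverse and Serious Adverse Events", and those members are not affiliated with the study; this partly mitigates the first exposure. The level-of-care judgment on failure to reach any abstinence rests on a 4-week window, so it largely comes before the draw. The other primary-outcome sources, patient-completed daily surveys and urine and breath tests, are less exposed than an interview.

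A reader might infer three stronger claims that the documents do not support:

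- *The trial was unblinded, or outcome raters see the levels.* No section says so.
- *The data-access list shows access during treatment.* It is a privacy statement and does not address timing.
- *The short half-life stated in the Risks section ("the plasma half life of Prazosin is 2-3 hours") shows that a low level usually means a late draw.* The plan gives neither the time from dose to draw nor a detection limit, so this cannot be shown, and the blinding point does not need it.

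**Conclusion.** Wrong as written: the instructions on prazosin levels and on blinding conflict, and nothing available reconciles them. Confidence is high on the conflict and on the missing statement of recipient and timing, subject to the pages that could not be checked.

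The consequence is conditional. If staff see levels during treatment, up to 9 of 12 weeks (75%) could be affected for an outpatient, assuming a draw at the start of week 4 and same-day results. The point concerns outpatients only, and neither their number nor the size of any bias can be computed. It should be corrected because the roles at risk feed safety attribution and one source of the primary outcomes. It is not evidence that the results are biased.

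**What to change.** Replace the sentence on use of the levels in the Outpatient Plan (Section V, item 3), and amend the matching sentence in Section VI, A.3, to read:

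> Prazosin levels will not be reported to blinded study staff or subjects before database lock; they will be released after lock for adherence analysis. The DSMB may obtain them earlier if needed for safety review. In-trial compliance monitoring by blinded staff will use the riboflavin marker present in both active and placebo capsules.

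Add the same exception for prazosin levels to the data-access statement in Section VIII, item f.

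The cost is wording in three places and one instruction to the laboratory on when to release results. No draw, visit or sample changes, and the levels stay available for adherence analysis. The loss is one in-trial check at a single time point, which could never verify adherence on placebo. The riboflavin check that remains has its own limits: it covers only the 2 to 8 hours after a dose and is judged by eye.

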One hundred and fifty treatment seeking alcohol dependent individuals (men and women) will be recruited to participate in this medication study. Subjects may or may not participate in laboratory sessions. Subjects will be recruited through flyers and advertisements in local newspapers and from community substance abuse treatment facilities. Subjects will participate in an initial screening and intake session to obtain informed consent, followed by physical examination and blood work to determine eligibility. Subjects will be randomized to Prazosin (PRZ) or placebo (PLA) and medication will be dispensed in a three times daily dosing schedule (t.i.d. dosing) with 5 mg in the morning, 5 mg in the afternoon and 6 mg at night reached at the end of the 2-week period, and maintained at this or their highest tolerated dose until week 11, followed by a 5-day taper in week 12, as in previous research. The titration schedule was as follows: 1 mg dose at bedtime for 2 nights, followed by a 1mg dose morning and night (8 AM/8 PM) on day 3, then 2 mg dose t.i.d., on days 4-6, 3 mg dose (2 pills each) morning and afternoon, and 4 mg dose (2 pills) at night for days 7-9, increased to 4 mg dosing t.i.d. on days 10-13, and from day 14 through week 11, 5 mg (1 pill) each in the morning and afternoon, and 6 mg for the night (2 pills) dose. Subjects will be maintained on this dose during the laboratory sessions (if completing the laboratory sessions) and until week 12 of the study at which point they will be tapered off the study medication over the course of five days. Some subjects may be tapered prior to completion of the 12 weeks. This taper is similar to what has been used with lofexidine in opiate withdrawal protocols (Bearn et al., 1996; Strang et al., 1997) and in our outpatient relapse prevention study of lofexidine with opiate dependent patients. We expect most subjects will tolerate a daily dose of 16.0mg. However, subjects who cannot tolerate a dosing schedule of 16.0 mg will meet with the study psychiatrist to discuss a reduction in dose down to 10mg/day. Based on the Physician Desk Reference (2007), which reports that dosage may be as high as 40mg daily, we anticipate that 16.0mg per day will be well tolerated by subjects. Subjects who cannot tolerate a minimum dose of 6mg/day will be removed from the study protocol.

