After a subject is able to abstain from substances for a period of 21+ days, they will have the option to complete a 3-night stay on the CNRU, where they will participate in imagery training and 3 laboratory sessions. After completion of the laboratory sessions, subjects will be discharged from the inpatient unit at least one day after the laboratory sessions.

Subjects will undergo the same titration onto study medication as outlined above. If the subject decides to complete the laboratory component, they will be maintained on 16.0mg dose of PRZ/PLA medication during the week of the inpatient laboratory sessions, after which they will undergo the above mentioned taper or continue to take their medication for 9 weeks in outpatient

treatment. In the event that someone continues to use alcohol while in the study, they may be asked to come in for more frequent appointments to assess for adverse symptomatology and meet with the study psychiatrist. Similar methods have been used in our outpatient lofexidine study and no adverse interaction events are anticipated.

Table 1: PRZ/PLA Dosing

	Prazosin PRZ (N = 75) (Male / Female)			Placebo (PLA) (N = 75) (Male / Female)		
Week 1	AM	PM	Evening	AM	PM	Evening
Days 1 -2 (1mg / 1mg)	0mg / 0mg	0mg / 0mg	1mg / 1mg	0mg / 0mg	0mg / 0mg	1mg / 1mg
Days 3 (2mg /1mg)	1mg / 0mg	0mg / 0mg	1mg / 1mg	1mg / 0mg	0mg / 0mg	1mg / 1mg
Days 4-6 (6 mg/4mg)	2mg/1mg	2mg/1 mg	2 mg/2mg	2mg/1mg	2mg/1 mg	2mg/2mg
Week 2						
Days 7-9 (10mg /8mg)	3mg / 2mg	3mg / 2mg	4mg /4mg	3mg / 2mg	3mg / 2mg	4mg /4mg
Days 10 – 13 (12mg/12mg)	4mg /4mg	4mg/4mg	4mg /4mg	4mg /4mg	4mg /4mg	4mg /4mg
Day 14 (16mg/16mg)	5mg/5mg	5mg/5mg	6mg/6mg	5mg/5mg	5mg/5mg	6mg/6mg

Follow-up:

Upon completion of outpatient treatment, follow-up interviews will be scheduled with all subjects. If a subject decides to complete only the inpatient phase, follow-up appointments will be scheduled after the inpatient phase is complete. Follow up interviews will be scheduled at 30 days. Urine monitoring, assessment of craving, cocaine abstinence symptoms, self report of drug use and stress and craving scales, will be assessed during the follow-up appointment.

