Simpson et al (2007) report that when administering 16mg per day of the drug, blood pressure changes were more evident in the prazosin group; however, the drop was still within the normal range. Raskind et al. 2002, prescribed up to 20mg a day of the study medication. Three of the 36 subjects reported orthostatic dizziness, headache, and lethargy, however no subject experienced syncope or a fall. The researchers report that previous administration of Prazosin for hypertension and benign prostate hypertrophy has shown that adverse effects tend to occur at initial lower doses rather than at higher doses. Raskind et al, 2007 used a maximum dosage of 15mg which was maintained for 8 weeks. No significant differences in supine or standing blood pressure were found between the placebo and Prazosin groups. Transient dizziness was reported by some subjects, however, most of these subjects were also receiving concurrent antihypertensive or psychotropic medication, and was also reported by subjects in the placebo group. Therefore, it appears that a maximum maintenance dosage of 16mg of prazosin will be generally tolerable and safe for use in the proposed adult sample of subjects.

3. **Source:** a) Identify the source of the drug or biologic to be used.

Commercially available Prazosin capsules will be used. Prazosin HCl (generic) is marketed by Mylan Pharmaceuticals Inc in capsules containing 1mg, 2mg, or 5mg of prazosin as the hydrochloride. The placebo medication will be prepared by the CMHC pharmacist. Both the Prazosin and the placebo will be dispensed by the CMHC pharmacist / YNHH IDS.

Prazosin pills will be purchased through the CMHC pharmacy / YNHH IDS, and the research pharmacist will make up identical active and placebo capsules for medication administration. Subjects will be randomly assigned to three times daily dosing of Prazosin/placebo (with the exception of day 1 which is once daily, and days 2-3 twice daily).

During weeks 1-4, inpatient subjects will self-administer study medication three times daily under supervision by nursing staff on the CNRU who will also monitor vital signs three times daily and side effects. Urines, alcohol craving, abstinence symptoms, mood and perceived stress scale and side effects will be assessed three times weekly.

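### The Section V.3 titration text and Table 1 (PRZ/PLA Dosing) give women different doses on days 3-9, and Section VI.A.3 gives a dosing frequency that conflicts with both on day 2

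*Combined protocol and SAP*

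**What the plan says.** The titration is described in three places.

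- **Section V.3, Research Plan (opening text).** One schedule, with no mention of sex. It begins with "1 mg dose at bedtime for 2 nights, followed by a 1mg dose morning and night (8 AM/8 PM) on day 3". The daily total is 6 mg, in three equal parts, over the next three days. It is 10 mg in the block after that, given as "3 mg dose (2 pills each) morning and afternoon, and 4 mg dose (2 pills) at night for days 7-9". The total is 12 mg/day on days 10-13 and 16 mg/day from day 14.
- **Section V.3, Table 1: PRZ/PLA Dosing** (not the later Table 1, the schedule of assessments). Each row has a male and a female figure. Days 1-2 are the same for both sexes ("Days 1 -2 (1mg / 1mg"). The figures then diverge: 2 and 1 mg on day 3, "Days 4-6 (6 mg/4mg" on the next row, and "Days 7-9 (10mg /8mg" after that. They coincide again at 12 mg on days 10-13 and 16 mg on day 14.
- **Section VI.A.3, Source.** Dosing is three times daily, "with the exception of day 1 which is once daily, and days 2-3 twice daily". No milligram amounts are given.

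The Outpatient Plan says, shortly before Table 1, that outpatients follow the titration already described. No section explains the split by sex or says which description governs.

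**The concern.** A pharmacist or nurse starting a woman on study drug finds a higher dose in the text than in the table for seven consecutive days. For every subject there is also a conflict over whether day 2 carries one dose or two. These instructions cannot all be followed.

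The drug lowers blood pressure, and the discrepancy falls in the initiation period. The protocol lists low blood pressure and dizziness as side effects and excludes hypotensive individuals. Section V.10 calls for additional vital-sign readings when the dose changes. For women the first change comes on day 3 under the text and on day 4 under Table 1, so the timing of that check depends on which place is read. Outpatients self-administer and attend twice a week, so a dispensing discrepancy might not be noticed the same day.

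A secondary point is reproducibility. Without one stated schedule, the nominal exposure of women in the prazosin arm during titration cannot be reported from the protocol.

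**Working it through.** **Inputs.** Morning, afternoon and night doses from the Section V.3 text; AM, PM and evening cells from Table 1 (PRZ/PLA Dosing), first figure male and second female; dosing frequency from Section VI.A.3.

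**Step 1. Reproduce Table 1's own totals.** Daily total = AM + PM + evening.

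- Men: 0+0+1 = 1; 1+0+1 = 2; 2+2+2 = 6; 3+3+4 = 10; 4+4+4 = 12; 5+5+6 = 16.
- Women: 0+0+1 = 1; 0+0+1 = 1; 1+1+2 = 4; 2+2+4 = 8; 4+4+4 = 12; 5+5+6 = 16.

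All six row labels are reproduced for both sexes, and the placebo columns carry the same split. The female column is therefore a coherent schedule, not a mistyped cell or a table broken in extraction.

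**Step 2. Compare the text with the table.** Excess for women = text total / female total − 1.

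| Days | Text (mg/day) | Table 1 men | Table 1 women | Text v women |
|---|---|---|---|---|
| 1-2 | 1 | 1 | 1 | 0% |
| 3 | 2 | 2 | 1 | +100% |
| 4-6 | 6 | 6 | 4 | +50% |
| 7-9 | 10 | 10 | 8 | +25% |
| 10-13 | 12 | 12 | 12 | 0% |
| 14 | 16 | 16 | 16 | 0% |

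Text and male column agree on every day.

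**Step 3. Cumulative dose for women.**

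- Days 1-9, text: 2×1 + 2 + 3×6 + 3×10 = 52 mg. Table 1: 2×1 + 1 + 3×4 + 3×8 = 39 mg. Ratio 52/39 = 1.33.
- Days 1-14 add 4×12 + 16 = 64 mg to each: 116 v 103 mg. Ratio 116/103 = 1.126, or 12.6% more.
- The absolute gap is 13 mg in both windows, since it arises entirely on days 3-9: 1 + 3×2 + 3×2 = 13.

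**Step 4. Doses per day.**

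| Day | Section V.3 text | Table 1 men | Table 1 women | Section VI.A.3 |
|---|---|---|---|---|
| 1 | 1 | 1 | 1 | 1 |
| 2 | 1 | 1 | 1 | 2 |
| 3 | 2 | 2 | 1 | 2 |

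Section VI.A.3 conflicts with every other source on day 2, and with Table 1 for women on day 3. On day 3 it agrees with the text and with the male column.

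**The case against.** The strongest reply is that the conflict is narrow and brief. In milligrams there are two versions. They differ for women only, on seven days, and in actual drug only within the prazosin arm, because placebo doses are nominal. The text is silent on sex and could be read as a summary that Table 1 refines. The largest relative figure, 100%, is 1 mg on one day. Safeguards apply under any version: the first dose is given at the clinic with one to two hours of observation, vital signs are monitored, and the dose can be reduced if not tolerated.

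Most of this stands as a limit on scope, but it does not remove the contradiction. No section says that Table 1 refines the text, and the Outpatient Plan's reference back to the titration already described weakens that reading. The safeguards reduce the consequences but do not tell the pharmacy what to dispense.

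A reader might infer more than the documents support in four ways:

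- *Three rival dose schedules.* Section VI.A.3 states frequency without amounts, so it is a conflicting remark and not a third milligram titration.
- *A dispute over the target dose.* Text and table are identical from day 10, and both reach 16 mg on day 14.
- *A documented hazard at the conflicting doses.* Section VI.A.2 relays other researchers' report that adverse effects tend to arise at the low starting doses. Text and table give the same dose on days 1-2, so that report does not show that 6 v 4 mg or 10 v 8 mg is where the risk lies.
- *A biased primary analysis.* The Section V.12 model treats weeks 1-2 as a separate pre-full-dose segment and includes gender as a control variable. Women's exposure in that segment would depend on the version used, but the documents give no basis for an effect on heavy drinking days or any drinking days.

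**Conclusion.** The contradiction is real and needs resolving. For women, the Section V.3 text gives 2, 6 and 10 mg/day on day 3, days 4-6 and days 7-9, where Table 1 gives 1, 4 and 8. The gap is 13 mg in total: 33% more over days 1-9 and 12.6% more over days 1-14 under the text. The frequency in Section VI.A.3 additionally conflicts on day 2 for everyone and on day 3 with the female column.

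The figures assume the Table 1 header order (male, then female), full adherence and no individual dose reduction. The milligram conflict is confined to women on days 3-9. The weight of the point lies in safe and reproducible dosing at initiation of a blood-pressure-lowering drug. Any effect on the weeks 1-2 model segment is secondary and is not quantified here. No view is taken on which schedule is right.

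**What to change.** Reconcile the Section V.3 text, Table 1 (PRZ/PLA Dosing) and Section VI.A.3 to one schedule, confirmed by the study physician and the pharmacy. State it once, in Table 1, with amount and frequency for each day, and say explicitly whether the difference by sex is intended; if it is not, remove it. Replace the schedules in the Section V.3 text and Section VI.A.3 with a reference to the table.

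Section V.3 introduces the titration in the past tense, so dosing may already have taken place. If it has, rewording is not enough: the study record should document which schedule was dispensed, for women in particular, and whether it changed during the trial.

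The cost is a protocol wording amendment and a check of the pharmacy worksheet, plus a review of dispensing records if subjects have already been dosed. Neither the sample size nor the analysis model needs to change.
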